17.6. PHYSICAL EXAMINATION

The count and percentage of patients with physical examination assessments will be summarized by body system and treatment group at schedule visit.

A patient-wise listing of physical examination findings will be provided.

17.7. NEUROLOGICAL EXAMINATION

The count and percentage of patients with neurological examination assessments will be summarized by system and treatment group at schedule visit.

A patient-wise listing of neurological examination findings will be provided.

17.8. OPHTHALMOLOGICAL EXAMINATION

The count and percentage of patients with ophthalmological examination assessments will be summarized by each type of assessment and treatment group at schedule visit.

A patient-wise listing of ophthalmological examination findings will be provided.

17.9. STRUCTURED SUICIDALITY ASSESSMENT

The count and percentage of patients with suicidality assessments will be summarized by system and treatment group at schedule visit.

A patient-wise listing of suicidality query will be provided.

17.10. TANNER STAGING

A patient-wise listing of Tanner staging will be provided.

18. DATA NOT SUMMARIZED OR PRESENTED

Not applicable.

Document:	\\ieedc-vnasc01\BIOSdata\Newron\Sarizotan\PXA76395\Biostatistics\Documentation\SAP		
Author:	[name]	Version Number:	V2
		Version Date:	[30March2020]
Template No:	CS_TP_BS016 – Revision 4	Reference:	CS_WI_BS005
Effective Date:	01Apr2016		

APPENDIX 1. PARTIAL DATE CONVENTIONS

Imputed dates will NOT be presented in the listings.

ALGORITHM FOR TREATMENT EMERGENCE OF ADVERSE EVENTS:

START DATE	STOP DATE	ACTION
Known	Known	If start date < study med start date, then not TEAE If start date >= study med start date, then TEAE
	Partial	If start date < study med start date, then not TEAE If start date >= study med start date, then TEAE
	Missing	If start date < study med start date, then not TEAE If start date >= study med start date, then TEAE
Partial, but known components show that it cannot be on or after study med start date	Known	Not TEAE
	Partial	Not TEAE
	Missing	Not TEAE
Partial, could be on or after study med start date	Known	If stop date < study med start date, then not TEAE If stop date >= study med start date, then TEAE
	Partial	Impute stop date as latest possible date (i.e. last day of month if day unknown or 31st December if day and month are unknown), then: If stop date < study med start date, then not TEAE If stop date >= study med start date, then TEAE

Document: \\ieedc-vnasc01\BIOSdata\Newron\Sarizotan\PXA76395\Biostatistics\Documentation\SAP

Author: [name]

Version Number:

V2

Version Date:

[30March2020]

Template No: CS_TP_BS016 – Revision 4

Reference: CS_WI_BS005

Effective Date: 01Apr2016

START DATE	STOP DATE	ACTION
	Missing	Assumed TEAE
Missing	Known	If stop date < study med start date, then not TEAE If stop date >= study med start date, then TEAE
	Partial	Impute stop date as latest possible date (i.e. last day of month if day unknown or 31st December if day and month are unknown), then: If stop date < study med start date, then not TEAE If stop date >= study med start date, then TEAE
	Missing	Assumed TEAE

ALGORITHM FOR PRIOR / CONCOMITANT MEDICATIONS:

START DATE	STOP DATE	ACTION
Known	Known	If stop date < study med start date, assign as prior If stop date >= study med start date and start date <= end of treatment, assign as concomitant
	Partial	Impute stop date as latest possible date (i.e. last day of month if day unknown or 31st December if day and month are unknown), then: If stop date < study med start date, assign as prior If stop date >= study med start date and start date <= end of treatment, assign as concomitant
	Missing	If stop date is missing could never be assumed a prior medication If start date <= end of treatment, assign as concomitant

Document: \\ieedc-vnasc01\BIOSdata\Newron\Sarizotan\PXA76395\Biostatistics\Documentation\SAP
 Author: [name]
 Version Number: V2
 Version Date: [30March2020]

Template No: CS_TP_BS016 – Revision 4
 Effective Date: 01Apr2016

Reference: CS_WI_BS005

START DATE	STOP DATE	ACTION
Partial	Known	
Impute start date as earliest possible date (i.e. first day of month if day unknown or 1st January if day and month are unknown), then:
 
If stop date < study med start date, assign as prior
 
If stop date >= study med start date and start date <= end of treatment, assign as concomitant

	Partial	
Impute start date as earliest possible date (i.e. first day of month if day unknown or 1st January if day and month are unknown) and impute stop date as latest possible date (i.e. last day of month if day unknown or 31st December if day and month are unknown), then:
 
If stop date < study med start date, assign as prior
 
If stop date >= study med start date and start date <= end of treatment, assign as concomitant

	Missing	
Impute start date as earliest possible date (i.e. first day of month if day unknown or 1st January if day and month are unknown), then:
 
If stop date is missing could never be assumed a prior medication
 
If start date <= end of treatment, assign as concomitant

Missing	Known	
If stop date < study med start date, assign as prior
 
If stop date >= study med start date, assign as concomitant

	Partial	
Impute stop date as latest possible date (i.e. last day of month if day unknown or 31st December if day and month are unknown), then:
 
If stop date < study med start date, assign as prior
 
If stop date >= study med start date, assign as concomitant

	Missing	Assign as concomitant

Document: \\ieedc-vnasc01\BIOSdata\Newron\Sarizotan\PXA76395\Biostatistics\Documentation\SAP
 Author: [name]
 Version Number: V2
 Version Date: [30March2020]

Template No: CS_TP_BS016 – Revision 4
 Effective Date: 01Apr2016
 Reference: CS_WI_BS005

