13 REPORTING SAFETY INFORMATION

13.1 Adverse Events

Adverse Event evaluations will be performed during the screening period, at baseline and at each visit of the study. Untoward medical events will be collected, from the time of signing of Informed Consent to the end of the safety follow-up period (14 days after last dose of study medication). All Adverse Events will be recorded in the CRF. In addition, all subjects will be followed up for 30 days after their last dose of study medication for the occurrence of any Serious AE.

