An Unexpected Adverse Drug Reaction is adverse event, the nature or severity of which is not consistent with the applicable product information (e.g., Investigator's Brochure for an unapproved investigational product or package insert/summary of product characteristics for an approved product).

Non-Serious Adverse Event

A non-serious adverse event is any adverse event that does not meet the criteria listed above for a serious adverse event.

Treatment-Emergent Adverse Events

Adverse events that are newly occurring or worsened in severity after administration of the study medication are considered to be treatment-emergent AEs (TEAEs). In the open-label extension period, only newly occurring AEs and AEs that were ongoing at Week 24 and worsen in severity will be considered TEAEs.

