15.2.5 Safety evaluations

All subjects who receive a dose of study medication will be included in the safety analyses. All adverse events will be listed and summarized by body system and preferred term. The incidence of AEs (%) and their relatedness to the study drug, as assessed by the Investigator, will be reported. Serious adverse events (SAEs) and events which are newly occurring or worsening after administration of the study medication (TEAEs) will be summarized. In addition, adverse events that result in death or discontinuation (ADOs) of the study medication will be listed separately.

Results for other safety parameters such as vital signs, laboratory parameters, ECGs, physical, neurological and ophthalmological examinations, and the suicidality assessment, will be listed and summarized accordingly. Changes from baseline in vital signs, ECG and laboratory values, and physical, neurological and ophthalmological examination findings will be summarized, with abnormal and clinically notable values/findings being identified. In the initial 24-week, double-blind, placebo-controlled period, a comparison will be made between the sarizotan and placebo groups in the proportion of subjects experiencing SAEs, ADOs, and TEAEs and any clinically significant abnormalities in other safety parameters. Where feasible, mean changes from baseline will be examined using a paired t-test. Safety data for the open-label extension period will be analyzed separately and will use the Week 24 evaluations from the double-blind period as the baseline assessments.

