17.1. ADVERSE EVENTS

Adverse Events (AEs) are be coded using MedDRA central coding dictionary version 22.0.

An AE is defined as any untoward medical occurrence in a patient or clinical investigation patient administered a pharmaceutical product that does not necessarily have a causal relationship with the product. An AE can therefore be any unfavorable and unintended sign (including a new, clinically important abnormal laboratory finding), symptom, or disease, temporally associated with drug administration, whether or not related to the product.

The above definition covers also cases of

- Exacerbation of pre-existing diseases or conditions.
- Pre-existing diseases or conditions (reported at time of screening in medical history) will not be considered AEs unless there is an increase in the frequency or severity, or a change in the quality of the disease or condition.
- Events occurring in subjects treated with matching placebo are also considered AEs.

An AE will be defined as a treatment-emergent adverse event (TEAE) if the first onset (or

Document:	\\ieedc-vnasc01\BIOSdata\Newron\Sarizotan\PXA76395\Biostatistics\Documentation\SAP		
Author:	[name]	Version Number:	V2
		Version Date:	[30March2020]

Template No: CS_TP_BS016 – Revision 4
 Effective Date: 01Apr2016

Reference: CS_WI_BS005

worsening, in the case of pre-existing disease) is after the first administration of study treatment throughout the study. In addition, any serious adverse events (SAEs) reported in the 30 days following last dose of IMP will be recorded and counted in the final clinical study report.

See [Appendix 1](#) for handling of partial dates for AEs. In the case where it is not possible to define an AE as treatment emergent or not, the AE will be classified by the worst case; i.e. treatment emergent.

An overall summary of number of subjects within each of the categories described in the subsection below, will be provided as specified in the templates. Listings will include TEAEs and Non-TEAEs. Listings will be provided for TEAEs, SAE and TEAEs leading to discontinuation from study for safety analysis set.

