17.1.6 ADVERSE DRUG REACTION (ADR)

All noxious and unintended responses to a medicinal product related to any dose should be considered as adverse drug reactions. ADR is a related event, so it is a TEAE that is related as defined in Section 17.1.3

A summary of ADR by SOC and PT will be prepared.

Any ADR during the study will be presented in a data listing.

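### SAP Appendix 1 sets the treatment-emergent flag from dates alone, so an AE that began in screening and worsened on treatment under its original start date is left out of the TEAE, serious-TEAE and ADR tables

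*SAP*

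**What the plan says.** The definition appears in several places and always includes worsening. Protocol 13.1.1 states: "Adverse events that are newly occurring or worsened in severity after administration of the study medication are considered to be treatment-emergent AEs (TEAEs". Protocol 15.2.5 says that "events which are newly occurring or worsening after administration of the study medication (TEAEs) will be summarized", and the synopsis safety analysis has the same content. SAP 17.1 accepts a first onset after dosing or, as the alternative, that the "worsening, in the case of pre-existing disease) is after the first administration of study treatment throughout the study".

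The flag itself is assigned in SAP Appendix 1, in the algorithm for treatment emergence. With a known start date the rule is "If start date < study med start date, then not TEAE", repeated for known, partial and missing stop dates. A second block, headed "Partial, but known components show that it cannot be on or after study med start date", returns not treatment-emergent for all three stop-date types. Where the start date is missing, or partial but possibly on or after first dose, the stop date decides: "If stop date >= study med start date, then TEAE". If the stop date is missing as well, the event is assumed treatment-emergent.

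On collection, Protocol 13.1 says: "Untoward medical events will be collected, from the time of signing of Informed Consent". AEs with a pre-dose onset will therefore be in the database. On reporting, SAP 17.1.6 says: "ADR is a related event, so it is a TEAE that is related". SAP 17.1.5 tabulates serious TEAEs, and SAP 17.1.7 leaves non-TEAEs to the listing.

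**The concern.** An operational rule should reproduce the definition it serves, and this one does not. SAP 3.3 declares no change from the protocol analysis, so the narrower rule does not read as a deliberate departure.

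The flag drives the TEAE tables by system organ class and preferred term, by intensity and by relationship (SAP 17.1.1 to 17.1.3), the serious-TEAE table (17.1.5) and the ADR table (17.1.6). Protocol 15.2.5 also promises a sarizotan versus placebo comparison of the proportion of patients with TEAEs. An event that starts in screening and becomes worse on drug is one form a harmful effect could take. If sarizotan did cause such worsening, the omission would fall more heavily on the active arms and narrow the difference from placebo. The documents neither show nor exclude that.

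**Working it through.** No sample-size or error-rate figure is involved. The check traces one case through the algorithm: an AE that began before first dose, worsened in severity after it, and ended after first dose or is ongoing. By the definitions in Protocol 13.1.1 and 15.2.5 and SAP 17.1, this is a TEAE.

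Appendix 1 has 4 start-date types and 3 stop-date types, so 4 × 3 = 12 cells. For this case they return:

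| Start date as recorded | Stop known | Stop partial | Stop missing |
|---|---|---|---|
| Known, before first dose | not TEAE | not TEAE | not TEAE |
| Partial, certainly before first dose | not TEAE | not TEAE | not TEAE |
| Partial, possibly on or after first dose | TEAE | TEAE | TEAE |
| Missing | TEAE | TEAE | TEAE |

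Six of the 12 cells contradict the definition and six agree with it. The pattern is also perverse: the same event counts when its start date is poorly recorded and is dropped when the date is exact.

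Next, does any other text correct the six cells?

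- The worst-case rule in SAP 17.1 applies only where emergence cannot be determined. A known pre-dose start is determined, so the rule does not reach it.
- Protocol 13.1.2 asks for the date and time the event started, and for separate records when episodes are separated in time. It gives no instruction to re-date or split a continuing AE whose severity rises.
- If a site nevertheless enters the worsening as a new AE dated at the worsening, the known-start row returns TEAE and nothing is lost.

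The loss therefore needs four conditions together: onset between consent and first dose (screening is Days -28 to -1 and may be shortened), still ongoing at dosing, severity increased on treatment, and one record kept under the original date.

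Size per event: the planned arm size is about 43, so one patient is 1/43 = 2.3 percentage points. This is a ceiling. A patient with another TEAE still counts in overall TEAE incidence, so the figure applies in full only to a table row in which the lost event was that patient's sole qualifying event. How many patients meet all four conditions cannot be derived from the documents.

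**The case against.** The best defence is that most clinically important worsening is already captured. Under Protocol 13.1.1 and SAP 17.1, a condition in the medical history becomes an AE only when it worsens, so its natural onset date is the date of worsening. Protocol 13.1.2 applies that logic explicitly to laboratory AEs, which start at the first sample showing the change. For seizures, Protocol 12.1.7 takes a history at screening and asks about changes at each later visit. This stands. A reader might infer that worsening seizures or breathing problems as a class are hidden, or that no AE starting before first dose can ever be treatment-emergent. The documents do not support either reading: long-standing problems may well be dated at the worsening, and six of the 12 cells return TEAE.

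It is also fair to say that the events do not disappear from safety reporting. Listings include non-TEAEs, the AE and SAE rows of the overview (SAP 17.1.1) are not worded as TEAE-only, and the discontinuation table (17.1.4) covers AEs. This stands too.

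A third argument is that SAP 17.1 refers to Appendix 1 only for partial dates, so 17.1 governs events with complete dates. That does not hold. The algorithm has its own rows for fully known dates, and the row for partial dates that are certainly pre-dose has the same defect. Two programmers, one working from 17.1 and one from Appendix 1, could produce different TEAE and ADR tables.

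Finally, whether a worsened AE keeps its old record may be settled in eCRF completion instructions that are not among the documents. That makes the loss conditional but leaves the contradiction in the SAP.

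**Conclusion.** Appendix 1 is wrong as written. For a known or certainly pre-dose start it returns the opposite of what the protocol and SAP 17.1 define when the event has worsened on treatment. The consequence is limited to AEs that arose between consent and first dose, were ongoing at dosing, worsened in severity and were kept under their original date. Those events would be missing from the TEAE, serious-TEAE and ADR tables, but not necessarily from the rest of the safety output.

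The number affected is unknown and could be zero. The ceiling of 2.3 points per patient assumes 43 patients per arm. Any statement about a shrunken difference between arms further assumes that worsening is more frequent on sarizotan, for which the documents give no figure. No efficacy conclusion is touched. This should be corrected before database lock, but it does not undermine the trial.

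**What to change.** In the Appendix 1 rows for a known start before first dose and for a partial start that must be before it, change the outcome to: not a TEAE unless severity increased on or after the first-dose date, in which case a TEAE with the date of worsening as its onset. Keep the criterion to severity, which is what Protocol 13.1.1 specifies.

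Before database lock, run a blinded data-management check of all AEs ongoing at Day 1 to find those that worsened and to date the worsening. State in the SAP whether the existing worst-case rule in 17.1 applies where a query cannot settle the matter.

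The text change is small. The real cost is some retrospective queries, because the AE form described in Protocol 13.1.2 lists one intensity per event and no date of change. SAP 3.1 describes randomization in the past tense and the extension as ongoing, so a new recording instruction to sites would come too late for double-blind data already entered. The SAP branch and the check therefore have to do the work. TEAE counts can only stay the same or rise.

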APPENDIX 2. CLINICALLY NOTABLE VALUES FOR LABORATORY PARAMETERS

Parameter	Synonym	S.I. units			Other units		
		Unit	Lower Limit	Upper Limit	Unit	Lower Limit	Upper Limit
Albumin		g/L	≤ 14	≥ 62	g/dL	≤ 1.4	≥ 6.2
Alk. Phosphatase	ALP	U/L	NA	≥ 3.0*URL			
Amylase		U/L	≤ 15	≥ 350			
ALAT, SGPT	ALT,GPT	U/L	NA	≥ 3.0*URL			
ASAT, SGOT	AST,GOT	U/L	NA	≥ 3.0*URL			
Bicarbonate		mmol/L	≤ 10	NA			
Bilirubin total		µmol/L	NA	≥ 34	mg/dL		≥ 2.0
Calcium total		mmol/L	≤ 2.1	≥ 3.0	mg/dL	≤ 8.2	≥ 12
Chloride		mmol/L	≤ 80	≥ 125			
Cholesterol		mmol/L	NA	≥ 7.25	mg/dL		≥ 280
Creatinine kinase	CPK	U/L	NA	≥ 3.0*URL			
Creatinine		µmol/L	NA	≥ 177	mg/dL		≥ 2.0
Gamma-GT Male		U/L	NA	≥ 100			
Female		U/L	NA	≥ 90			
Globulin total		g/L	≤ 10	NA			
Glucose		mmol/L	≤ 1.7	≥ 13.9	mg/dL	≤ 30	≥ 250
LDH		U/L	NA	≥ 3.0*URL			
Phosphate		mmol/l	NA	≥ 2			
Potassium		mmol/L	≤ 2.5	≥ 6.5			
Protein total		g/L	≤ 45	NA			
PTT		sec	NA	≥ 80			
Sodium		mmol/L	≤ 120	≥ 165			
Triglycerides		mmol/L	NA	≥ 5.6	mg/dL		≥ 500
Urea		mmol/L	NA	≥ 16.6	mg/dL		≥ 100
Urea nitrogen	BUN	mmol/L	NA	≥ 84.0	mg/dL		≥ 30
Uric acid Male		µmol/L	NA	≥ 624	mg/dL		≥ 10.5
Female		µmol/L	NA	≥ 505	mg/dL		≥ 8.5

Document: \\iecdc-vnasc01\BIOSdata\Newron\Sarizotan\PXA76395\Biostatistics\Documentation\SAP
 Author: [name] Version Number: V2
 Version Date: [30March2020]

Template No: CS_TP_BS016 – Revision 4
 Effective Date: 01Apr2016

Reference: CS_WI_BS005

Parameter	Synonym	S.I. units			Other units		
		Unit	Lower Limit	Upper Limit	Unit	Lower Limit	Upper Limit
Basophils		L/L	NA	≥ 0.15	%		≥ 15
Eosinophils		L/L	NA	≥ 0.10	%		≥ 10
Erythrocytes Male	RBC	10 ¹² /L	≤ 2.5	NA			
Female		10 ¹² /L	≤ 2.0	NA			
ESR Male		Mm	NA	≥ 25			
Female		Mm	NA	≥ 35			
Hematocrit Male	EVF	L/L	≤ 0.37	NA	%	≤ 37	
Female		L/L	≤ 0.32	NA	%	≤ 32	
Hemoglobin Male		g/L	≤ 115	NA	g/dL	≤ 11.5	
Female		g/L	≤ 95	NA	g/dL	≤ 9.5	
Leukocytes	WBC	10 ⁹ /L	≤ 2.8	≥ 16.0			
Lymphocytes		L/L	NA	≥ 0.80	%		≥ 80
MCHC		mmol/L	≤ 12.4	≥ 27.9	g/dL	≤ 20	≥ 45
MCV		10 ⁻¹⁵ L	≤ 60	≥ 120			
Monocytes		L/L	NA	≥ 0.40	%		≥ 40
Neutrophils		L/L	≤ 0.15	NA	%	≤ 15	
Thrombocytes	Platelets	10 ⁹ /L	≤ 75	≥ 700			

CLINICALLY NOTABLE URINALYSIS VALUES

Variable	Clinically Notable Values
Protein	Increase of 2 units
Glucose	Increase of 2 units

Document: \\ieedc-vnasc01\BIOSdata\Newron\Sarizotan\PXA76395\Biostatistics\Documentation\SAP
 Author: [name]
 Version Number: V2
 Version Date: [30March2020]

Template No: CS_TP_BS016 – Revision 4
 Effective Date: 01Apr2016

Reference: CS_WI_BS005

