The Investigator must review screening laboratory values prior to the first administration of the study agent, to ensure that the subject meets the protocol's inclusion/exclusion criteria. The Investigator must review post-dose laboratory values within 24 hours of receipt of the laboratory report. After the review is completed, the Investigator must sign and date each laboratory report.

The laboratory will provide normal reference ranges for the laboratory tests on the laboratory results report. A value is **normal** when it falls on or within the upper and lower limits of the reference range. A value is **abnormal** when it exceeds the upper or lower limit of the reference range. The laboratory will flag all abnormal and clinically notable values (defined in [Appendix 2](#)) on the laboratory report, will provide the normal reference ranges for each parameter, and will verify that the result is not due to pre-analytical problems (e.g., sample taken improperly, sample stored incorrectly, sample labeled incorrectly) or to analytical problems (e.g., machine not accurately calibrated, technical problems with equipment or reagents, or deterioration of analyte).

In cases where a patient is unable to get to the clinic for a scheduled laboratory test, or when a follow-up laboratory test is required for safety reasons, the test may be performed by a local laboratory, rather than the central laboratory designated for the study. The results of the test(s) performed by the local laboratory will be reported to the Investigator, and a copy of the laboratory report will be included in the patient's study file.

The Investigator must evaluate any change of *clinical relevance* from pre-dose to post-dose in a laboratory test as to whether it meets the definition of an adverse event, and repeat, if needed, any clinically significant abnormal laboratory test. Any laboratory abnormalities meeting the definition of an adverse event should be recorded on the Adverse Events CRF.

Refer to [Section 13.0](#), "Reporting Safety Information" for further directions.

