19.2 APPENDIX 2: Clinically Notable Values

The following guidelines, originally established by the Division of Neuropharmacological Drug Products of the FDA, will be used for determining clinically notable values for laboratory and vital signs parameters.

NOTABLE VALUES FOR LABORATORY PARAMETERS AND VITAL SIGNS

CLINICALLY NOTABLE BLOOD CHEMISTRY VALUES

Parameter	Synonym	S.I. units			Other units		
		Unit	Lower Limit	Upper Limit	Unit	Lower Limit	Upper Limit
Albumin		g/L	≤ 14	≥ 62	g/dL	≤ 1.4	≥ 6.2
Alk. Phosphatase	ALP	U/L	NA	≥ 3.0*URL			
Amylase		U/L	≤ 15	≥ 350			
ALAT, SGPT	ALT,GPT	U/L	NA	≥ 3.0*URL			
ASAT, SGOT	AST,GOT	U/L	NA	≥ 3.0*URL			
Bicarbonate		mmol/L	≤ 10	NA			
Bilirubin total		μmol/L	NA	≥ 34	mg/dL		≥ 2.0
Calcium total		mmol/L	≤ 2.1	≥ 3.0	mg/dL	≤ 8.2	≥ 12
Chloride		mmol/L	≤ 80	≥ 125			
Cholesterol		mmol/L	NA	≥ 141	mg/dL		≥ 500
Creatinine kinase	CPK	U/L	NA	≥ 3.0*URL			
Creatinine		μmol/L	NA	≥ 177	mg/dL		≥ 2.0
Gamma-GT Male		U/L	NA	≥ 100			
Female		U/L	NA	≥ 90			
Globulin total		g/L	≤ 10	NA			
Glucose		mmol/L	≤ 1.7	≥ 13.9	mg/dL	≤ 30	≥ 250
LDH		U/L	NA	≥ 3.0*URL			
Phosphate		mmol/l	NA	≥ 2			
Potassium		mmol/L	≤ 2.5	≥ 6.5			
Protein total		g/L	≤ 45	NA			
PTT		sec	NA	≥ 80			
Sodium		mmol/L	≤ 120	≥ 165			
Triglycerides		mmol/L	NA	≥ 5.6	mg/dL		≥ 500
Urea		mmol/L	NA	≥ 16.6	mg/dL		≥ 100
Urea nitrogen	BUN	mmol/L	NA	≥ 84.0	mg/dL		≥ 30
Uric acid Male		μmol/L	NA	≥ 624	mg/dL		≥ 10.5
Female		μmol/L	NA	≥ 505	mg/dL		≥ 8.5

Amend. 1, 19Jan2016; Amend. 2, 18May2016; Amend. 3, 21Oct2016; Amend. 4, 03Mar2017; Amend. 5, 29Mar2017; Amend. 6, 13Apr2017; Amend. 7, 02Oct2017; Amend. 8, 02Nov2017; Amend. 9, 11Feb2018; Amend. 10, 29Nov2018; Amend. 13, 10Dec2019; Amendment 14, 17 March 2020, Clean, Final

CLINICALLY NOTABLE HEMATOLOGY VALUES

Parameter	Synonym	S.I. units			Other units		
		Unit	Lower Limit	Upper Limit	Unit	Lower Limit	Upper Limit
Basophils		L/L	NA	≥ 0.15	%		≥ 15
Eosinophils		L/L	NA	≥ 0.10	%		≥ 10
Erythrocytes	RBC	10 ¹² /L	≤ 2.5	NA			
	Female	10 ¹² /L	≤ 2.0	NA			
ESR	Male	Mm	NA	≥ 25			
	Female	Mm	NA	≥ 35			
Hematocrit	Male	EVF	L/L	≤ 0.37	NA	%	≤ 37
	Female		L/L	≤ 0.32	NA	%	≤ 32
Hemoglobin	Male		g/L	≤ 115	NA	g/dL	≤ 11.5
	Female		g/L	≤ 95	NA	g/dL	≤ 9.5
Leukocytes	WBC	10 ⁹ /L	≤ 2.8	≥ 16.0			
Lymphocytes		L/L	NA	≥ 0.80	%		≥ 80
MCHC		mmol/L	≤ 12.4	≥ 27.9	g/dL	≤ 20	≥ 45
MCV		10 ⁻¹⁵ L	≤ 60	≥ 120			
Monocytes		L/L	NA	≥ 0.40	%		≥ 40
Neutrophils		L/L	≤ 0.15	NA	%	≤ 15	
Thrombocytes	Platelets	10 ⁹ /L	≤ 75	≥ 700			

CLINICALLY NOTABLE URINALYSIS VALUES

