17.3. LABORATORY EVALUATIONS

Results from the central laboratory will be included in the reporting of this study for hematology, clinical chemistry, urinalysis, thyroid function tests, virology, serum pregnancy test for post-pubertal females, HPA axis and prolactin. A list of laboratory assessments to be included in the outputs is included in the protocol.

Quantitative laboratory measurements reported as “< X”, i.e. below the lower limit of quantification (BLQ), or “> X”, i.e. above the upper limit of quantification (ULQ), will be converted to X for the purpose of quantitative summaries, but will be presented as recorded, i.e. as “< X” or “> X” in the listings.

Document:	\\ieedc-vnasc01\BIOSdata\Newron\Sarizotan\PXA76395\Biostatistics\Documentation\SAP		
Author:	[name]	Version Number:	V2
		Version Date:	[30March2020]
Template No:	CS_TP_BS016 – Revision 4	Reference:	CS_WI_BS005
Effective Date:	01Apr2016		

The following summaries (descriptive statistics for quantitative measurements and count and percentage for qualitative measurements except urinalysis) will be provided for laboratory parameter (i.e. hematology, clinical chemistry, urinalysis, HPA axis, Serum Pregnancy Test and prolactin).

- Actual and change from baseline by visit (for quantitative measurements).
- Shift from baseline to Week 24 and End of Study visits according to standard normal range criteria (for quantitative measurements and categorical measurements).
- Incidence table at Week 24 and End of Study visits according to clinically notable values (for quantitative measurements and categorical measurements).
- Listing of subjects' laboratory evaluations with flagging of abnormal values.

The descriptive statistics for actual measurement and change from baseline by treatment group will be performed at scheduled visits.

17.4. 12-LEAD ECG

ECG analysis related details can be found in ECG SAP.

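### The notable-value limits for urea nitrogen do not convert between their two unit columns in either appendix, and the protocol's cholesterol limits contradict both each other and the SAP's

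*SAP*

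**What the plan says.** Each document carries its own Appendix 2 of clinically notable laboratory values, with an SI column and, for many analytes, a second column in conventional units.

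- **Urea nitrogen.** The SAP's SI limit is "Urea nitrogen BUN mmol/L NA ≥ 84.0"; the whole row, with its mg/dL limit, reads "Urea nitrogen BUN mmol/L NA ≥ 84.0 mg/dL ≥ 30". The protocol prints the same two limits.
- **Cholesterol, protocol.** "Cholesterol mmol/L NA ≥ 141 mg/dL ≥ 500".
- **Cholesterol, SAP.** "Cholesterol mmol/L NA ≥ 7.25 mg/dL ≥ 280".

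The limits are put to use in two places. Protocol 12.1.5 states: "The laboratory will flag all abnormal and clinically notable values", and refers to protocol Appendix 2 for the definition. SAP 17.3 plans an "Incidence table at Week 24 and End of Study visits according to clinically notable values", without naming an appendix or a unit column. Urea nitrogen and total cholesterol both belong to the biochemistry panel (protocol 11.4.1 and Table 7). SAP section 1 says the SAP is based on the protocol dated 17 March 2020, which is the current one, and SAP 3.3 lists no changes to the analysis from the protocol.

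**The concern.** Two limits printed side by side for one analyte should be the same concentration in different units. If they are not, whether a result counts as notable depends on the column that was programmed. If two current documents give different limits, the label the site sees and the count in the safety table can disagree for the same sample.

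At stake is the notable category for two analytes. An SI urea nitrogen limit set far too high would leave an empty line in the incidence table whatever the data, and that zero could be read as reassurance about a renal marker. For cholesterol, a result could be counted in the SAP table without having been labelled notable to the investigator.

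**Working it through.** **Formula.** mmol/L = (mg/dL × 10) / molar mass; the inverse is mg/dL = mmol/L × molar mass / 10.

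**Inputs.** The limits come from the two appendices. Molar masses are not in the documents and are taken as physical constants (g/mol): urea 60.06; nitrogen per mole of urea 28.014; nitrogen atom 14.007; cholesterol 386.65. The documents do not say whether mmol/L of urea nitrogen counts urea molecules or nitrogen atoms, so both are shown.

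**Control.** The same formula was applied to ten other paired limits: bilirubin, calcium (low and high), creatinine, glucose (low and high), triglycerides, urea, and uric acid (male and female). The ratio of printed to converted SI value lies between 0.99 and 1.03 for all ten. For urea, 100 × 10 / 60.06 = 16.65, printed as 16.6. The method therefore reproduces the rest of the table.

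**The rows at issue.**

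| Row | Printed SI (mmol/L) | Printed mg/dL | mg/dL limit converted to mmol/L | Printed / converted | Printed SI converted to mg/dL |
|---|---|---|---|---|---|
| Urea nitrogen, as urea | 84.0 | 30 | 30 × 10 / 28.014 = 10.71 | 7.84 | 235 |
| Urea nitrogen, as N atoms | 84.0 | 30 | 30 × 10 / 14.007 = 21.42 | 3.92 | 118 |
| Cholesterol, protocol | 141 | 500 | 500 × 10 / 386.65 = 12.93 | 10.90 | 5,452 |
| Cholesterol, SAP | 7.25 | 280 | 280 × 10 / 386.65 = 7.24 | 1.00 | 280 |

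**Likely origin for urea nitrogen.** 30 × 2.8 = 84.0 exactly, while the conversion on the urea convention is 30 / 2.8 = 10.7. That pattern suggests multiplication in place of division, and it explains the ratio: 2.8 × 2.8 = 7.84.

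**Zones of disagreement.**
- Urea nitrogen, same in both documents: from 10.7 to below 84.0 mmol/L (30 to 235 mg/dL) a result is notable in the mg/dL column and not in the SI column. On the nitrogen-atom convention the zone is 21.4 to below 84.0 mmol/L (30 to 118 mg/dL).
- Cholesterol, between documents: in mg/dL, 280 to 499 is notable under the SAP and not under the protocol (500 / 280 = 1.8-fold). In SI, 7.25 to below 141 mmol/L is notable under the SAP and not under the protocol (141 / 7.25 = 19.4-fold).

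**The urea row does not settle the intended limit.** 16.6 mmol/L of urea corresponds to 16.6 × 2.8014 = 46.5 mg/dL of urea nitrogen, which matches neither printed limit. Urea as such is not in the study panel; urea nitrogen is.

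**The case against.** The strongest reply concerns consequence. A reader might infer that a high urea nitrogen or cholesterol would go unseen. The documents do not support that. Protocol 12.1.5 has the laboratory flag every value outside the reference range, print the ranges, and have the investigator review each report within 24 hours of receipt and assess clinically relevant changes as possible adverse events. SAP 17.3 adds shift tables by normal range and listings that flag abnormal values. Creatinine, also in the panel, has limits that convert correctly. This objection stands: the loss is confined to the notable label and its line in one descriptive table.

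Second, neither document states the laboratory's reporting units or the column programmed. If mg/dL is used, the urea nitrogen rule works as printed. This also stands, and it makes the practical effect conditional.

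Third, a reader might infer that 10.7 mmol/L is the right limit and that 84.0 is simply wrong. The arithmetic makes an inverted conversion likely, but it shows only that the two columns disagree. The intended limit is for the sponsor to state.

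Fourth, SAP 17.3 does not name its appendix, whereas SAP 17.5 expressly names Appendix 3 for vital signs. That the laboratory table will use SAP Appendix 2 is a reasonable inference, not a stated fact.

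None of this removes the inconsistency. The urea nitrogen figures appear identically in both documents, so a text-extraction fault is not a plausible explanation, and neither convention for mmol/L reconciles them.

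**Conclusion.** The point holds as two separate defects.

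1. Urea nitrogen: the unit columns disagree 7.8-fold (mmol/L as urea) or 3.9-fold (as nitrogen atoms). The defect is the same in both documents, so it depends on units alone. If the SI column is programmed, the notable flag and its incidence line would in practice never be triggered.
2. Cholesterol: the protocol's own pair disagrees 10.9-fold, and both of its limits differ from the SAP's, with no change declared in SAP 3.3. The SAP pair is internally consistent. That does not show it to be the intended limit, only that it needs no unit correction.

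The factors rest on standard molar masses and, for urea nitrogen, on the convention stated. The effect on actual flags rests on the unit column in use and on the inference that the SAP table follows the SAP appendix. The efficacy analyses and the testing sequence are untouched. The correction is worth making because the figures are operative and cheap to put right.

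**What to change.** - The sponsor confirms the intended notable limit for urea nitrogen and for cholesterol.
- Print matching SI and mg/dL values for each in both appendices. If 30 mg/dL of urea nitrogen is intended, the SI equivalent is 10.7 mmol/L expressed as urea; state the convention.
- In SAP 17.3, name the appendix and unit column that define a notable laboratory value.
- Record the cholesterol difference in SAP 3.3, or remove it by aligning the documents.
- Check which column the central laboratory and the SAP programmers have loaded, and re-run affected flags before the final analysis.

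The cost is a few table cells, one sentence in SAP 17.3, one entry in SAP 3.3, and a programming check. The number of labels that would change cannot be judged from the documents; it depends on the limits confirmed and the units in use.
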